7.4 EHR-based Prognostic Decision Support (P2)

For enrolled subjects assigned to the decision support arm, providers will receive prognostic information derived using our previously validated and best performing model. The decision support application will automatically calculate predicted risk for moderate (intensive care) and severe (respiratory failure or shock) outcomes using the parameters derived from the prognostic tool’s regression equation. Outcome probabilities will be integrated into the decision support application and displayed within the EHR. The support application will also report any objective criteria necessitating hospitalization (e.g., hypoxia) or potential intensive care (e.g., hypotension, SpO₂<92% despite FiO₂≥ 50%) to further inform site of care decisions. The application will also query providers regarding factors influencing site of care decisions to inform analyses describing discrepancies between risk assessments and decision-making (e.g., hospitalization of low risk children) and provider variation in risk tolerance. *Importantly, the tool will offer prognostic information only and will not proscribe a specific site of care or management plan. All site of care decisions will remain at the discretion of the treating provider.*

Table 2. Appropriate Site of Care Definitions

Disposition	Appropriate if:
Home care	No subsequent hospitalization within 24h
Inpatient, ward	Hospital length of stay ≥ 24h; or hospital length of stay < 24h but objective criteria for admission present (eg, need for supplemental oxygen); and no subsequent transfer to ICU within 24h
Inpatient, ICU	ICU length of stay ≥ 24h; or ICU length of stay < 24h but objective criteria for ICU admission present (eg, respiratory failure)

h, hours; ICU, intensive care unit

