8.5 Analysis (P2)

Logistic regression models will be performed to compare appropriate site of care disposition between the two study arms, controlling for important baseline covariates (e.g., age, season, provider type) to maximize power. Robust standard errors will be calculated to account for hospital clustering effects. We will also perform analyses to assess for interactions between two study arms and predicted risk for severe outcomes, age, provider type, and initial site of care, to identify subgroups in whom decision support may be most useful. Similar analyses will be conducted for the proposed secondary and exploratory outcomes along with cox regression model for hospital length of stay outcome.

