#### **6.1.2 Phase 2**

To test the hypothesis that the delivery of severity information generated by our prognostic tool leads to more appropriate site of care disposition compared to usual care.

The primary outcome is appropriate site of care disposition (Table 2). Surveillance for subsequent ED visits and hospitalizations to our institutions as well as escalation to higher levels of care will be captured within the EHR data extracted by the decision support application. Secondary efficacy and safety outcomes include the overall site of care disposition (ED discharge, ward, ICU), and ED revisits and hospitalizations within 72 hours and 7 days of the index discharge.

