### **6.3.2 Phase 2**

During the 24-month study period, randomization will occur at the patient level. Allocation to intervention or control will be based on medical record number (even vs. odd) and will be assigned automatically once the treating provider confirms the diagnosis of pneumonia and eligibility. We expect participants will be randomized (1:1). The providers of intervention subjects will receive prognostic information derived using our previously validated and best performing model. Providers of control arm subjects will not receive this information but will have access to all clinical data. Participants will be blinded to the treatment assignments and study staff and providers will not be blinded to treatment arm assignments due to the nature of the interventions.

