### **11.1 Primary Objective**

The primary objective (PO 1) of the study is to compare proportions of appropriate overall site of care disposition with or without EHR-based prognostic decision support in children 0.6-17 years of age presenting for emergency care. The hypothesis for this primary objective is that the proportion of appropriate site of care disposition is higher in the group receiving EHR-based prognostic decision support vs. the group receiving usual care. This information is captured through chart review and entered in the REDCap database. An investigator in both Nashville and Pittsburgh will be in charge of outcome assessment review, blinded to intervention assignment, and will decide whether site of care disposition is appropriate, yes (1) or no (0), based on Appendix 2 table for this analysis.

The proportions will be compared between the intervention arm versus the control arm using a Cochran-Mantel-Haenszel method in a stratified analysis by site to control for two sites at the alpha 0.05 level. The proportion difference and corresponding 95% confidence interval for concordance of antibiotics with or without adjusting for sites will also be calculated.

We will conduct a multivariable logistic regression model to compare appropriate site of care disposition between the two study arms, controlling for important baseline covariates. Important baseline covariates (e.g., age, sex, race, site, season, month, frequency of bacteremia and other pneumonia-related complications) will also be assessed and included as model covariates. Robust standard errors will be calculated to account for hospital clustering effects. We will also perform analyses to assess for interactions between two study arms and predicted risk for severe outcomes, age, provider type, and initial site of care, to identify subgroups in whom decision support may be most useful.

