### Appropriate Site of Care Definitions

Disposition	Appropriate if:
Home care	No subsequent hospitalization within 24h
Inpatient, ward	Hospital length of stay $\geq$ 24h; or hospital length of stay $<$ 24h but objective criteria for admission present (eg, need for supplemental oxygen); and no subsequent transfer to ICU within 24h
Inpatient, ICU	ICU length of stay $\geq$ 24h; or ICU length of stay $<$ 24h but objective criteria for ICU admission present (eg, respiratory failure)

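### The planned Phase 2 arm-by-initial-site-of-care interaction conditions on a decision made after the risk display, so its strata are not randomised comparisons

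*SAP*

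**What the plan says.** The Phase 2 primary analysis is a Cochran-Mantel-Haenszel comparison stratified by hospital, followed by a covariate-adjusted logistic model (SAP 11.1). The same section adds tests of "interactions between two study arms and predicted risk for severe outcomes, age, provider type, and initial site of care". Protocol 8.5 has the same list and states its purpose: "predicted risk for severe outcomes, age, provider type, and initial site of care, to identify subgroups in whom decision support may be most useful".

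Four other statements fix where site of care stands in the sequence of events:

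- **Allocation.** SAP 6.3.2: the arm "will be assigned automatically once the treating provider confirms the diagnosis of pneumonia and eligibility".
- **Display.** Protocol 7.4: "For enrolled subjects assigned to the decision support arm, providers will receive prognostic information derived using our previously validated and best performing model". The application also reports objective criteria for admission or intensive care "to further inform site of care decisions".
- **Hypothesis.** SAP 6.1.2: delivering the severity information "leads to more appropriate site of care disposition compared to usual care".
- **Outcomes.** Protocol 7.5 and SAP 6.1.2 list the disposition itself (ED discharge, ward or ICU) as a secondary outcome, although SAP 5.2 words that item as appropriate disposition. The primary outcome in Appendix 2 has a separate rule for each disposition. For home care, for example, it is "No subsequent hospitalization within 24h".

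Neither document defines initial site of care or describes recording an intended disposition before the risk is shown.

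**The concern.** A subgroup analysis keeps the protection of randomisation only if subgroup membership cannot be affected by the arm. Age meets that condition. Initial site of care, read as ED disposition, does not. If the tool works as hypothesised, some children who would have gone to the ward under usual care go home, or the reverse. The ward children in one arm are then not the counterparts of the ward children in the other.

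The difficulty is compounded because the same variable chooses the scoring rule. A child who moves from ward to home leaves one stratum, enters another and is judged by a different criterion. Differences between strata then mix any effect on appropriateness with a change in who is in each stratum. The stated aim is to learn in whom the tool is most useful, and this term cannot answer that. It could point to the wrong group.

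**Working it through.** **The plan's own Phase 2 figure.** Inputs from SAP 6.2.2: 1000 per arm, 90% appropriate under usual care, alpha 0.05, 80% power, detectable difference 3.4 points. Two-sided testing is assumed because the sidedness is not stated.

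n per arm = [1.96·√(2·0.917·0.083) + 0.842·√(0.90·0.10 + 0.934·0.066)]² / 0.034² ≈ 1033.

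With 1000 per arm the power for 3.4 points is 78.7%, and 80% power corresponds to 3.45 points. The stated figure stands as a rounding. It is not in dispute and only sets the scale.

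**Assumed control arm.** The documents give no counts by disposition. For illustration, per 1000: home 588/600 appropriate, ward 270/350, ICU 42/50. The total is 900/1000, which matches the 90% in SAP 6.2.2. ICU is left unchanged throughout.

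**Check 1: no effect on any child's appropriateness.** The tool moves m ward children who would have been scored appropriate to home, where they are again scored appropriate. Overall stays at 90.0%. In the ward, the 80 inappropriate children remain:

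- ward proportion = (270 − m)/(350 − m)
- ward OR = [(270 − m)/80] / [270/80] = (270 − m)/270
- home proportion = (588 + m)/(600 + m)

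| m | Ward, control → tool | Ward OR | Home, control → tool | Overall |
|---|---|---|---|---|
| 25 | 77.1% → 75.4% | 0.91 | 98.0% → 98.1% | 90.0% in both arms |
| 50 | 77.1% → 73.3% | 0.81 | 98.0% → 98.2% | 90.0% in both arms |
| 100 | 77.1% → 68.0% | 0.63 | 98.0% → 98.3% | 90.0% in both arms |

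The ward appears to be harmed although no child's score has changed.

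**How often the interaction test would flag this.** Each arm of 1000 was drawn from the multinomial distribution implied above, 1000 trials per value of m. The home log OR minus the ward log OR was divided by √(sum of 1/cell over the eight home and ward cells) and tested at |z| > 1.96.

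| Children moved per 1000 | 0 | 25 | 50 | 100 | 150 |
|---|---|---|---|---|---|
| Rejections | 4.5% | 4.9% | 9.6% | 27.5% | 61.8% |

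**Check 2: a real benefit overall.** The tool moves m ward children with brief stays and no objective criteria (scored inappropriate) to home, and a fraction q of them are hospitalised within 24 hours.

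- m = 36, q = 5%: home (588 + 34.2)/636 = 97.8%, OR 0.92. Ward 270/314 = 86.0%, OR 1.82. Overall (622.2 + 270 + 42)/1000 = 93.4%.
- m = 50, q = 30%: home (588 + 35)/650 = 95.8%, OR 0.47. Ward 270/300 = 90.0%, OR 2.67. Overall (623 + 270 + 42)/1000 = 93.5%.

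The overall result improves by about the design difference, while the home stratum reads as harm. The harm is an artefact: the moved children improved on balance, but they join a home stratum that was already at 98%.

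**The case against.** **The term is undefined and might mean something fixed earlier.** This has limited force. Every child is enrolled in the ED, so location at enrolment cannot separate them, and the only site categories in the documents are home, ward and ICU. A disposition intended before display would be legitimate, but no such item is described.

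**The distortion is small unless the tool moves many children.** This stands. With 25 moved per 1000 the test stays near its nominal level, and with 50 it rejects in about 10%. Large error rates need 100 or more moved. How many will move is unknown, and the error grows the more the tool changes practice.

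**A reader might infer that the tool could look helpful in every subgroup while worsening care overall.** That is too strong. Take assumed counts of 650 home at 97%, 300 ward at 78% and 50 ICU at 90%, with 100 home children (95% appropriate there) moved to the ward, where 92% score appropriate. Home goes from 97.0% to 97.4%, ward from 78.0% to 81.5% and overall from 90.95% to 90.65%. ICU is unchanged, so not every subgroup improves. The 95% intervals for the three changes all include zero (overall −0.3 points, −2.8 to +2.2), and the interaction test on these counts gives chi-square 0.13 on 2 df, p = 0.94.

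**A reader might infer that predicted risk has the same flaw.** The documents do not support this. The score is built from variables available at presentation (Protocol 3.0). The calculation sentence in Protocol 7.4 names no arm, although its paragraph opens with the decision support arm. SAP 6.3.2 withholds only the display from control providers, and data collection includes data elements from the decision support applications (Protocol 7.3, SAP 7.1). Protocol 4.2 describes as similar another trial that calculates risk for all and shows it for half. Computed alike in both arms, the score gave 4.6% to 6.0% rejection in simulation, which is valid. If it were missing in controls, the interaction could not be estimated, which is not a reversal. What remains is an unstated detail about whether and when the score is computed for controls.

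**A reader might infer that these tests decide where the tool is deployed.** No passage says so. The stated purpose is only to identify where it may be most useful.

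**Conclusion.** The concern holds for initial site of care. Read as ED disposition, it follows allocation and display, is the tool's target, is listed as an outcome and indexes the primary outcome rule. Its interaction with arm is not a baseline subgroup analysis, and its stratum contrasts can mislead in size and direction.

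The size depends on assumed stratum counts and numbers moved. With no effect on any child's appropriateness, the spurious ward OR runs from 0.91 to 0.63 for 25 to 100 children moved per 1000, with about 5% to 28% false rejection. The structural fault does not depend on those counts.

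The scope is limited to the additional interaction analyses. The Cochran-Mantel-Haenszel comparison is untouched. For predicted risk only a clarification is warranted.

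**What to change.** 1. Delete initial site of care from the interaction list in SAP 11.1 and Protocol 8.5. If a subgroup of this kind is wanted, replace it with an intended disposition recorded in both arms before any risk is displayed.
2. Report the primary outcome by actual disposition as description only, without an interaction test.
3. As a clarification, state that predicted risk is computed and stored in both arms, undisplayed in controls, from data up to the same pre-display time and with the same rule for missing inputs.

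The first two changes are text edits and need no extra patients or visits. The cost is that there will be no inferential subgroup result by disposition. The replacement in step 1 would add one provider question at confirmation of the diagnosis. Step 3 needs control-arm logging only if the application does not already do it, which the documents do not say.

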### **11.2 Secondary Objectives**

There are three secondary objectives for this study.

- a) The first secondary objective (SO 1) is to compare proportions of appropriate site of care disposition, by EHR-based prognostic decision support or usual care.

The analysis is similar to primary objective 1 though proportions of appropriate site of care disposition is the outcome.

- b) The second secondary objective (SO 2) is to compare proportions of participants having ED revisits and hospitalizations within 72 hours of the index discharge, by EHR-based prognostic decision support or usual care.

Proportions of participants having ED revisits or hospitalizations within 72 hours of the index discharge will be compared between intervention and control arms using Chi-square tests. Proportions and difference of proportions between intervention and control arms will be reported along with their 95% CIs.

Two multivariable logistic regression models clustering by hospitals will be conducted. The outcomes are ED revisits (yes or no) and hospitalizations (yes or no) within 72 hours of the index discharge and covariates under the consideration will be similar to the ones listed in the primary objective analysis 11.1.

- c) The third secondary objective (SO 3) is to compare proportions of participants having ED revisits and hospitalizations within 7 days of the index discharge, by EHR-based prognostic decision support or usual care.

The analysis is similar to secondary objective 2 though proportions of having ED revisits and hospitalizations within 7 days of the index discharge are the outcomes.

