8.6 Potential Limitations and Alternative Approaches (P2)

In contrast to our studies of antibiotic decision support, we chose to randomize at the individual level rather than monthly crossovers since potential for contamination effects is minimal (i.e. risk estimates are unique to each individual's set of circumstances and linked to a complex algebraic equation). Although we hypothesize that supplying providers with objective prognostic information will improve care decisions, this information could lead to unintended outcomes, such as increased hospitalizations in low risk children. This would be an important finding in itself, as it contrasts with prior studies in adults highlighting the usefulness of adult pneumonia severity tools, and provides valuable data regarding how risk information is interpreted and applied.

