### **3 PROTOCOL OBJECTIVES FOR PHASE 2**

#### **3.1 Primary**

- a) PO 1: To compare proportions of appropriate overall site of care disposition with or without EHR-based prognostic decision support in children with emergency care aged 0.6-17 years.

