#### **3.2 Secondary**

- a) SO 1: To compare proportions of appropriate site of care disposition, by EHR-based prognostic decision support or usual care.
- b) SO 2: To compare proportions of participants having ED revisits and hospitalizations within 72 hours of the index discharge, by EHR-based prognostic decision support or usual care.
- c) SO 3: To compare proportions of participants having ED revisits and hospitalizations within 7 days of the index discharge, by EHR-based prognostic decision support or usual care.

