### **5 STUDY OUTCOME MEASURES FOR PHASE 2**

#### **5.1 Primary**

- a) POM 1.1: Proportions of appropriate overall site of care disposition with or without EHR-based prognostic decision support in children 0.6-17 years presenting for emergency care. Please see Appendix 2 for the definition of appropriate site of care disposition (an investigator in both Nashville and Pittsburgh will be in charge of review, blinded to intervention assignment).

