#### **5.2 Secondary**

- a) SOM 1.1: Proportions of appropriate site of care disposition, by EHR-based prognostic decision support or usual care.
- b) SOM 2.1: Proportions of participants having ED revisits within 72 hours of the index discharge, by EHR-based prognostic decision support or usual care.  
SOM 2.2: Proportions of participants having hospitalizations within 72 hours of the index discharge, by EHR-based prognostic decision support or usual care.
- c) SOM 3.1: Proportions of participants having ED revisits within 7 days of the index discharge, by EHR-based prognostic decision support or usual care.  
SOM 3.2: Proportions of participants having hospitalizations within 7 days of the index discharge, by EHR-based prognostic decision support or usual care

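### Phase 2 secondary objective 1 in the SAP repeats the primary endpoint, so the protocol's three-level site-of-care disposition is never compared by arm

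*SAP*

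**What the plan says.** Protocol 2.0 and 7.5 define the Phase 2 primary outcome as appropriate site of care, scored by Table 2. Both then list further outcomes, and SAP 6.1.2 uses the same words: "Secondary efficacy and safety outcomes include the overall site of care disposition (ED discharge, ward, ICU", followed by ED revisits and hospitalizations at 72 hours and 7 days.

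The operative SAP sections read differently.

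- SAP 3.2, SO 1: "To compare proportions of appropriate site of care disposition, by EHR-based prognostic decision support or usual care".
- SAP 5.2, SOM 1.1: "Proportions of appropriate site of care disposition, by EHR-based prognostic decision support or usual care".
- SAP 11.2(a): "The analysis is similar to primary objective 1 though proportions of appropriate site of care disposition is the outcome".
- The primary in SAP 3.1 is "To compare proportions of appropriate overall site of care disposition with or without EHR-based prognostic decision support", and in SAP 5.1 it is "Proportions of appropriate overall site of care disposition with or without EHR-based prognostic decision support". SAP 11.1 codes it yes/no from Appendix 2.

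Protocol 8.5 adds a general commitment: "Similar analyses will be conducted for the proposed secondary and exploratory outcomes along with cox regression model for hospital length of stay outcome".

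**The concern.** The primary and SO 1 differ only by the word *overall*. In the protocol that word belongs to the secondary outcome. The SAP has a single definition of appropriateness (Appendix 2), so SO 1 as written re-runs the primary, and the disposition outcome has no objective, measure or method.

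Disposition is the most direct reading of what the tool does to admission and ICU use. Protocol 8.6 warns that "this information could lead to unintended outcomes, such as increased hospitalizations in low risk children" and says this would be an important finding. Appendix 2 registers that harm only in part. A ward stay under 24 hours without objective criteria counts as inappropriate. An unneeded ward stay of 24 hours or more, with no ICU transfer within 24 hours, counts as appropriate. The two arms could therefore match on the primary while admitting different proportions of children.

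**Working it through.** **1. Match the secondary outcomes one by one.**

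| Protocol 7.5 and SAP 6.1.2 | SAP 3.2, 5.2, 11.2 |
|---|---|
| Disposition: ED discharge, ward, ICU | SO 1: appropriate site of care, yes/no (same as the primary) |
| Revisits and hospitalizations, 72 hours | SO 2: matches |
| Revisits and hospitalizations, 7 days | SO 3: matches |

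The second and third rows agree, so SO 1 is the place for disposition.

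**2. Look for disposition elsewhere in the Phase 2 analyses.** SO 2 and SO 3 count events after the index discharge. EO 1 is death. EO 2 is length of stay among hospitalized children only. SAP 11.1 uses initial site of care as an effect modifier, not an outcome. The SAP 9.1 table does not list disposition. Nothing fills the gap.

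**3. Reproduce the plan's own power figure.** Inputs from Protocol 8.4 and SAP 6.2.2: n = 1,000 per arm, 90% appropriate under usual care, alpha 0.05 (taken as two-sided), difference 3.4 points. With p̄ the mean of the two proportions:

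- s0 = √[2p̄(1−p̄)/n] and s1 = √{[p1(1−p1) + p2(1−p2)]/n}
- power = Φ[(d − 1.96·s0)/s1] + Φ[(−d − 1.96·s0)/s1]

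For 0.900 v 0.934, s0 = 0.01234 and s1 = 0.01231, so power = Φ[(0.034 − 0.02418)/0.01231] = Φ(0.797) = 78.7%. The detectable increase at 80% power is 3.45 points. This agrees closely with the plan and confirms the formula.

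**4. Ask how well each endpoint would detect extra admissions.** Assumptions, none given in the documents:

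- The tool raises admission by 5 points.
- The extra children would otherwise have had an appropriate home discharge, and nothing else changes.
- A share b of the extra admissions is brief and lacks objective criteria.

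The primary then falls by 0.05 × b:

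| b | Primary, control v intervention | Power |
|---|---|---|
| 10% | 0.900 v 0.895 | 6.6% |
| 33% | 0.900 v 0.8835 | 22.1% |
| 50% | 0.900 v 0.875 | 42.4% |
| 100% | 0.900 v 0.850 | 92.3% |

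The direct comparison of any admission does not depend on b. The control rates of 19%, 31% and 69% are the national low, median and high in Protocol 1.0, not rates for the two study sites. The row at 47.5% is the minimum over that range.

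| Any admission, control v intervention | Power | b above which the primary is more powerful |
|---|---|---|
| 0.19 v 0.24 | 77.7% | 0.79 |
| 0.31 v 0.36 | 65.9% | 0.68 |
| 0.475 v 0.525 | 60.9% | 0.64 |
| 0.69 v 0.74 | 69.8% | 0.71 |

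**5. Vary the 5 points.** At a 2-point rise the direct comparison has only about 15% to 20% power over the same control rates. The break-even share is more stable, at about 0.62 to 0.80 for rises of 2 to 8 points.

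**The case against.** Several points can be made for the plan.

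- *The outcome is not abandoned.* SAP 6.1.2 names it, and Protocol 8.5 promises similar analyses for secondary outcomes. Both are true. But the methods referred to are for a yes/no outcome, and neither document states how three levels would be compared. The SAP contradicts itself as well as the protocol.
- *Admission counts would be visible anyway.* The denominators of the length-of-stay comparison and the interaction with initial site of care would show how many children were admitted in each arm. This is so, but neither is a planned comparison with an estimate and confidence interval.
- *SO 1 may mean appropriateness within each disposition, with the primary pooled.* The SAP does not say so, and disposition would still lack an analysis under that reading. The authors should confirm what they intended.
- *The power figures rest on an unsourced 5-point rise.* This stands. At small rises both endpoints are weak. If the tool reduced some admissions while raising those of low-risk children, the net admission rate could also stay flat, and only a breakdown by predicted risk would show the harm. The interaction of arm with predicted risk in SAP 11.1 helps a little, but it acts on the primary outcome.

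**Conclusion.** The concern holds, and it rests on the text alone. An efficacy and safety outcome named in the protocol, and in the SAP's own study description, has no objective, measure or analysis in the SAP. Its slot duplicates the primary. The likeliest cause is a drafting slip in which *overall* moved from the secondary outcome to the primary.

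The power figures only illustrate what is lost. Under the stated assumptions, a direct comparison of admissions is the more sensitive of the two unless roughly 64% to 79% or more of the extra admissions are brief and lack criteria. The documents do not give that share. The Phase 2 primary analysis is unaffected. The correction should be made before the data are analysed, because otherwise the three-level method would be chosen afterwards.

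**What to change.** 1. In SAP 3.2, 5.2 and 11.2(a), restate SO 1 and SOM 1.1 as the distribution of index disposition (ED discharge, ward, ICU) by arm.
2. Remove *overall* from the primary in SAP 3.1, 5.1 and 11.1, once the authors confirm that no separate meaning was intended. The Appendix 2 definition does not change.
3. Name one site-adjusted three-level model in advance. Multinomial or ordinal logistic regression would both serve; the team used the ordinal form for its severity scale (Protocol 3.0). Report risk differences with 95% confidence intervals for any admission and for ICU.
4. Optionally, report any admission by arm across predicted risk, which addresses the Protocol 8.6 concern most directly.

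The cost is SAP wording and one or two models. Site of care is already collected (SAP 7.1), and the interaction in SAP 11.1 already requires predicted risk in both arms. The primary endpoint, sample size and alpha stay as they are, since SAP 7.2 makes no alpha adjustment for secondary analyses.
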